6.5.6 Participant enrollment and handling

Every effort will be made to arrange routine clinical follow-up for all participants, independent of how many study-associated visits they have completed.

Enrolment into study will take place at the two participating hospital departments (Department of Dermatology, Bispebjerg University Hospital and Department of Dermatology and Venereology, Sahlgrenska University Hospital).

The total duration of the study from enrolment of first participant to end of data collection is expected to be 1.5 years.

Expected total duration of each participants' participation is 9 months, with milestone evaluation after every 3 months.

In total 20 participants will be enrolled (target enrolment is 10 participants at Department of Dermatology, Bispebjerg University Hospital and 10 participants at Department of Dermatology and Venereology, Sahlgrenska University Hospital). Enrolment is not stratified. Limits can be changed based on the coordinating investigators discretion if recruitment to one study group turns out being not possible or according to experience unrealistic. Enrolment is based on participants remitted to the centers for diagnosis and treatment of NF1. Participants with urgent treatment need are not enrolled.

Participants of the study continue their course and normal registration in the hospital department. Each study visit is registered and documented in the hospital file parallel to registrations in the case reports of the study.

Histology taken at the Swedish center will be labeled using the study codes which do not contain the personal identification number of the study person. The samples will be used only for research purpose and not for patients care and treatment. The samples will be analyzed separately by a pathologist and the PI in Sweden. After the analyses the samples will be stored in Biobank Väst in Sahlgrenska Universitetssjukhuset,

6.6 Procedures

The study will be conducted according to the requirements of Good Clinical Practice (GCP) as per ISO 14155:2020.

The study personnel will inform the participants verbally and in a participant information document in the respective local language on the experimental procedure to be utilized, and assure the participants that their decision regarding participation in the study will have no bearing on the quality of medical care received, and that their decision whether to participate in the study is strictly voluntary.

During the initial interview, the participants will be assured that they are free to change their mind and will be allowed to participate in the study or withdraw from the study with no adverse effect on their standard medical care. Participants will have at least 24 hours to consider their consider their participation.

The study personnel will obtain written Informed Consent prior to the participants' participation in any study procedure.

The investigational device is described in detail in the investigator's brochure. The device is used in the study as described in the brochure. The two devices used in the study are identical and validated to be so by the equipment supplier.

The standard choice of hand piece will typically be those with a focal point depth of 1.8 or 2.3 mm. The hand piece depth shall match the estimated thickness of the tumor best possible. The hand piece with focal depth 1.8 mm will be preferred for treatment on the extremities, where the skin is known to be relatively thin. For treatments on the trunk, where skin is known to be thicker, the hand piece with focal depth of 2.3 mm will be preferred. The choice will be guided by tumor size and thickness of the overlying skin, location, and the investigator can decide to use hand piece best suited for the case. The tumor shall preferably be exposed to ultrasound down to the bottom of the tumor, but not so deep as to increase risk of post-treatment scarring. The selected hand piece applied for each tumor is documented in the CRF.

Prior to the HIFU treatment, the selected area will be sterilized with an alcohol swab and the selected area will be outlined with a pen where necessary. The tumor will be documented by a photo, repeated immediately post treatment, and at the planned visits after 1-week, 3 months and 9 months.

HIFU treatment will primarily be administered with shot-duration of 150 milliseconds, as this has been demonstrated in an animal safety study and in human treatments to be effective, and at the same time sufficiently short to avoid disturbing effects from movement of the hand piece during energy delivery.

HIFU power will be selected dependent on treatment site and skin response in initial test shots applied to the tumor. Power levels between 4 to 9 W acoustic power is the range of operation of the device. The acoustic energy dosage will, thus, be in the range of 0.6 to 1.3 J/shot.

On-going ex-vivo results will be used to validate these treatment guidelines and potentially adjust accordingly. Adjustments, if relevant, will not exceed existing certified clinical settings or existing standard limitations of the device.

The investigator can decrease or increase the energy level guided by the visual assessment of the observed treatment dose effect in the tumor. A HIFU-dose shall produce an immediate visible whitening or contraction of a circular area sized about 1-2 mm around the target center. This is observed through the integrated dermoscope allowing direct control of the treated field. Dosing is applied as shoulder-by-shoulder covering the entire tumor and 2 - 3 mm of perilesional skin, immediately around the tumor, with 1-2 mm between each dose. The investigator can choose to treat the surrounding (non-thickened) skin with lower energy to save normal tissue and minimize the post-treatment wound.

The treatment of a cNF, which is in the range of 2 - 12 mm in horizontal width, is expected to require approximately 25 - 50 shots spaced nearby each other, "shoulder-by-shoulder". Elapse between shots is some 2 - 3 seconds. The total direct time for a treatment is, thus, estimated to be not more than 5 minutes, including small pauses to monitor the treatment effect and the need of adjustment of device setting. The total time for the treatment session is estimated to be in the range 20 - 40 min.

The equipment supplier is responsible for control and maintenance of the investigational device during the study including check of the energy output.

The equipment supplier has a third device in stock available for the study in case of instrument breakdown of a study device during study.

Clinical recording of the study includes clinical assessment of healing and therapeutic effect on the tumors. Such assessment follows clinical criteria described in textbooks, guidelines and clinical consensus in the specialty of dermatology. Prior to study, the two investigator sites have coordinated their clinical assessment method.

The chosen 9-month total study period is considered acceptable for observation of tolerance and curative effect of HIFU for cNF with observation of primary therapeutic effect after 3 months. Assessments includes monitoring of the wound healing phase, observation of late recurrences, and observation of scarring.

The study includes no follow up medication, but the study can involve use of wound healing dressings and other remedies in the wound healing phase on investigators individual recommendation. The study involves no standard recommendation on post treatment care, which is anticipated to be simple.

After the study participants are followed in the respective hospital departments according to their needs and the department routines.

Participants who drop out of the study before the 3-month visit voluntarily or for non-medical reasons, including non-adherence, will be replaced by new participant(s). Withdrawals after 3 months are replaced on investigators discretion with considerations to the impact of the overall investigation schedule.

Patient with incomplete cure documented by ultrasound imaging assessment or biopsy and histology after 3 months or subsequent control visit (indicated by clinical suspicion of reoccurrence) will be offered a second treatment based on the standard treatment offered by the center. The specific treatment will be decided by the investigator and the patient based on the extent and severity of the recurrence.

The study will conclude when all participants have completed the 9-month study period, when all data are on file, and the statistical analysis is concluded. Interim analysis of data collected after 3 months and later is allowed, per investigator's decision.

If the study design is deemed inferior, the protocol can be amended.

The study produces no physical test samples relevant for purposes outside the study.

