1.1 Summary of the clinical investigation

The overall objective of this study is to evaluate the safety, tolerability, and efficacy of cutaneous neurofibromas (cNF) removal in adults with Neurofibromatosis Type 1 (NF1) using high-intensity focused ultrasound (HIFU).

With an incidence of 1/2500 to 1/3500, Neurofibromatosis Type I (NF1) is among the most common single-gene inherited conditions worldwide (1, 2). The genetic condition predisposes to multiple forms of histologically benign and malignant neoplasms. The most common tumor across all people with NF1 is cutaneous neurofibroma (cNF), impacting up to 99% of adults (3-7). These tumors can number in the hundreds to thousands on a given individual, most often appear between late school age and in the second decade, and increase in number and size across the lifespan (3-5, 8-12).

In many patients, cNF are socially debilitating, painful and impede activities of daily living (4, 5, 10-14). Multiple different appearances of cNF exist as reported from patients and clinicians. These can range from barely visible flat nodules with subtle discoloration, to large and pedunculated masses. One proposed classification system to describe the clinical appearance of cNF assigns one of five subcategories: nascent, flat, sessile, globular, or pedunculated (15). Nascent lesions (very small dispersed tumors) and peduncular neurofibromas (protruding tumors with a narrow base) are not subject to study as they are not logic candidates for HIFU treatment at this early stage. The typical appearance of the cNF-categories relevant for treatment in this study is illustrated in Fig. 1.

Despite the remarkable prevalence of cNFs in people with NF1 and their documented influence on quality of life (QoL), current treatment is limited to surgical removal or the use of various devices that cause tissue destruction showing mixed, but largely low-efficacy success, to date (11, 16-18).

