While blade-based surgical removal allows complete removal of the lesion(s), this method is impractical to address the many tumors affecting a typical adult with NF1, thus forcing patients to select specific tumors to remove. Additional drawbacks of surgical resection include variable scarring, and the time required for the procedure and healing. Alternative approaches that enable the removal of larger numbers of lesions per session include electrosurgical ablation, laser-based treatments, and radiofrequency ablation all reported to have variable outcomes(11, 15-17, 19-22).

[figure not shown]

Fig. 1. Three subtypes of cutaneous neurofibromas considered for the current study.

The investigational device used in this study is a Danish developed system. As the first of its kind in the world, it is capable of controlled and targeted thermo-mechanical treatment to small intradermal volumes containing neoplastic cells, without inflicting damage to the surrounding tissue (23-26).

The device is proposed to be used in a non-ablative modality, where treatment does not damage the skin's basement membrane, and the skin surface thereby remain intact. Healing after treatment will thus be facilitated by internal cell transport through the vasculature, and risks of post-treatment complications or visible scarring will be minimized (23-25, 27).

The current protocol presents an investigation with an evaluation of the safety and efficacy profile 3 months after a single 3-5 minute treatment. Subsequent follow-up of secondary endpoints is done every third month until the end of the study 9 months after the treatment. The activities of the investigation are summarized in Table 1, and a graphic presentation of the patient-flow and actions are given in Fig. 2.

Provided that the expected positive clinical results can be verified, this new method could have potential for widespread use as an important replacement or compliment to existing methods for treatment of cNF.

RECRUITMENT (Pre-study)	NF1 Patients with Cutaneous Neurofibro	
ACCEPTANCE & REGISTRATION (Visit 1)	cNFs for treatmen (Inclusion Criteria) min. 5 pcs	t Exit (Exclusion Criteria)
TREATMENT (Visit 2)	Photo / US (DK) HIFU min. 3 pcs 2 + Photo / US (DK)	Control
WEEK 1 (Visit 3)	Photo US (DK)	^{2 pcs} Photo US (DK)
MONTH 3 (Visit 4)	min. 2 pcs Photo US (DK)	1 pcs Photo US (DK)
MONTH 6 (Visit 5)	Photo US (DK)	1 pcs Photo US (DK)
MONTH 9 (Visit 6)	min. 1 pcs Photo US (DK)	1 pcs Photo US (DK)

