The hypothesis of this study is, that small and highly localized acoustic focal zones produced by a new HIFU device non-invasively can induce acute cell-death in cutaneous neurofibromas (cNF) without disrupting the skin's basement membrane. The healing of the treated volume will subsequently be facilitated by internal cell-transport through the vasculature without creation of open wounds. This therapeutic modality will thus give less post-treatment complications and less visible scarring compared to surgical procedures that are currently the only standard treatment for removal of cNFs in patients carrying the Neurofibromatosis Type 1 genetic condition.

The objective of the study is therefore to document that 20 MHz focused ultrasound is safe and effective in the treatment of NF1 associated cNF with high reduction of the measured volume of each treated tumor after 3 months, and with follow up registration of potential regrowth or development of new tumors in the treated and untreated regions at 6 and 9 months.

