5.1 Primary endpoint - Tolerability

- The grade of any adverse events (AE) requiring medical intervention within three months of treatment should be low. Device-based treatment will be considered tolerable if less than 30% of participants treated have an "Overall AE Score" larger than Grade 2 AE at the 3month follow-up (visit 4) as assessed via Common Terminology Criteria for Adverse Events (CTCAE), U.S. Department of health and human services, Ver 5.0, Nov 27, 2017.
- The rate and nature of spontaneous healing of the treated cNF lesion and any safety related event including potential wound formation and wound healing should be equivalent to expectations from alternative method(s). Safety evaluation includes rating of treatment associated sequele by end of study, e.g. dyspigmentation and scarring and overall investigator rating compared to expectations.

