5.2 Secondary endpoints – Efficacy, safety and feasibility

- Efficacy: Rate of clearance, e.g. reduction of tumor mass of treated cNFs based on 2D and 3D photography or ultrasound imaging assessment at 3 and 9 months parallel to assessment of the degree of dyspigmentation with hypermelanosis or hypomelanosis of the lesion and the perilesional untreated skin.
- Safety: Itch and pain from the treatment measured on a 0-10 point numerical scale.
- Safety: Wheal and flare reaction and inflammatory responses are measured on a graded scale.
- Safety: Any objective adverse effect or event, local or systemic, related to the treatment and the investigational device is measured (wound and course of wound healing, scar formation, instrumental hazards) is categorized immediately after treatment and at all follow-up visits.
- Feasibility: Feasibility is evaluated both quantitatively (time spent on treatment) and qualitatively depending on the object considered and cover elements that may compromise or favor HIFU relative to other treatments employed for lesions in clinical practice or from the literature. Feasibility assessment will not produce a direct comparison with alternative methods since the study has no arm with an alternative method. The evaluation comprise the following essentials:
 - 1) Time and resource spent on the treatment session using the device,
 - 2) Investigators' assessment of the practice of using the device and the treatment,
 - 3) Participants" assessment of satisfaction with the treatment and the device.

All skin toxicities will be grated according to the classifications in Common Terminology Criteria for Adverse Events (CTCAE), U.S. Department of health and human services, Ver 5.0, Nov 27, 2017.

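### Tumours that fail HIFU can get another treatment from month 3, and no rule keeps that treatment out of the 9-month clearance and late scarring results

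*Combined protocol and SAP*

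**What the plan says.** Section 6.6 makes the offer to participants with incomplete cure shown by ultrasound or by histology "after 3 months or subsequent control visit". Such a participant "will be offered a second treatment based on the standard treatment offered by the center", and the investigator and patient choose the treatment. Nothing postpones it until after the 9-month visit.

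Three later assessments fall after the offer opens:
- Efficacy in section 5.2 is clearance or reduction of tumour mass, "based on 2D and 3D photography or ultrasound imaging assessment at 3 and 9 months".
- Section 5 plans "follow up registration of potential regrowth or development of new tumors in the treated and untreated regions at 6 and 9 months".
- Section 5.1, under the tolerability heading, adds: "Safety evaluation includes rating of treatment associated sequele by end of study", with dyspigmentation and scarring as examples.

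Section 6.6 does not name the second treatment. Section 5 refers to "surgical procedures that are currently the only standard treatment for removal of cNFs", and section 1.1 says that "current treatment is limited to surgical removal or the use of various devices that cause tissue destruction". Table 1 plans one HIFU session only.

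Section 7 covers sample size, power and possible pooling by tumour. It contains no rule for a tumour treated a second time.

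**The concern.** The re-treated tumours are selected because HIFU did not clear them. How they count at month 9 is therefore not neutral: the result depends on a choice that the plan leaves open and that could be made after the data are seen. The study is open-label, and section 6.6 allows interim analysis at the investigator's decision.

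Two results are at stake. One is 9-month clearance, which would inform whether larger studies follow. The other is late scarring and dyspigmentation. The hypothesis in section 5 is that HIFU scars less than surgery, yet a surgical mark on a re-treated tumour may be present when sequelae are rated at visit 6.

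**Working it through.** **No plan figure to reproduce.** The calculations in section 7 concern the AE proportion only. The first one reproduces: 1.96² × 0.90 × 0.10 / 0.15² = 15.37, so 16. None concerns clearance.

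**Timing.** The offer can open at visit 4 (3 months) or visit 5 (6 months). A tumour re-treated then comes before the visit 6 assessment. A re-treatment decided at visit 6 itself does no harm. The visit 4 AE grade and 3-month clearance are recorded before any re-treatment.

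**Two readings of the current text.**
- *The participant stays in.* Section 6.6 does not mention withdrawal, so the tumour is measured at visit 6 as it then is.
- *The participant is withdrawn.* Section 6.5.2 excludes patients receiving other therapy for their cNF, and 6.5.3 makes an exclusion criterion that arises on study a ground for withdrawal. Section 6.5.4 removes data from analysis only for withdrawals before 3 months. Later withdrawals may be replaced at the investigator's discretion. The failures then have no 9-month result.

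**Illustration.** Let p be clearance by HIFU alone, r the share of uncleared tumours re-treated before visit 6, and s the clearance by the second treatment.
- Counted as not cleared: p
- Left out: p / [p + (1 − p)(1 − r)]
- As observed: p + (1 − p) r s

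| p | r | s | Not cleared | Left out | As observed |
|---|---|---|---|---|---|
| 20% | 50% | 100% | 20% | 33% | 60% |
| 50% | 50% | 100% | 50% | 67% | 75% |
| 50% | 50% | 50% | 50% | 67% | 62.5% |
| 80% | 50% | 100% | 80% | 89% | 90% |
| 80% | 25% | 100% | 80% | 84% | 85% |

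Second row: 0.50; 0.50 / (0.50 + 0.50 × 0.50) = 0.667; 0.50 + 0.50 × 0.50 × 1 = 0.75.

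All p, r and s values are assumptions. Two have an anchor in the documents: p = 20% is the stopping limit in 6.5.5, taken here per tumour, and s = 100% follows the remark in 1.1 that blade surgery can remove a lesion completely.

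**Withdrawal acts on participants, not tumours.** A withdrawn participant's cleared tumours leave as well, so the left-out column can overstate the effect. Take p = 50%, three tumours each, and half of the participants with any failure withdrawn without replacement.
- If a participant's tumours all respond alike, the result is 67% as above.
- If they respond independently, 0.5³ = 12.5% of participants have all three cleared. The other 87.5% average (0.5 − 0.125) / 0.875 = 42.9%. After half of those leave, clearance is (0.125 + 0.4375 × 0.429) / (0.125 + 0.4375) = 55.6%.

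Both exceed 50%.

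**Exposure.** With the minimum of three treated tumours in Table 1, Denmark follows 10 × 3 = 30 to month 9. Sweden follows 10 × (3 − 2 biopsied) = 10, because section 6.3.2 treats biopsied tumours as lost to follow-up. That makes 40. Section 7 speaks of at least four tumours per participant, which gives 40 + 20 = 60. The percentages in the table do not depend on this count.

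**The case against.** **Withdrawal already handles it.** Sections 6.5.2 and 6.5.3 can be read so that a re-treated participant leaves the study and has no visit 6 result. That reading is open, but it does not close the gap. Section 6.6 makes the offer without mentioning withdrawal, and removing failures with discretionary replacement also raises clearance.

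**Not every tumour is exposed.** A reader might infer that both centres are equally affected. The documents do not support that. In Sweden incomplete cure is documented by biopsy, and the biopsied tumour is then out of follow-up. Unbiopsied Swedish tumours are exposed only if the offer extends beyond the tumour that was sampled, which 6.6 does not say. Denmark is the clear case.

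**Scars can be attributed.** A reader might infer that a surgical scar would be scored against HIFU. Section 5.1 rates sequelae associated with the treatment, and the investigator knows what was done. The text supports possible confounding, not certain misattribution.

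**The second treatment might be HIFU.** Section 6.6 does not rule it out in words. Sections 1.1 and 5 and the single session in Table 1 point to another method. A repeat HIFU session would also need a rule, because the plan evaluates one session.

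**It is a small first study with its main effect at 3 months.** True, and this limits the consequence. The final report still concludes the endpoints after the 9-month visit.

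**Conclusion.** The point holds for 9-month clearance and, more weakly, for scarring, dyspigmentation and AE grade recorded after month 3. Under either reading of the plan, 9-month clearance is biased upward. This assumes that some participants accept the offer before visit 6 and either that the second treatment clears some tumours or that those withdrawn had done worse than average.

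The size is not known. In the assumed middle case clearance reads 50%, 67% or 75% according to the rule used. If HIFU clears 80%, the spread is at most 10 percentage points in the cases shown. None of these is a forecast.

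Because sequelae stand under the primary endpoint heading, a reader might infer that the primary result is compromised. It is not: the numeric tolerability criterion is the AE grade at visit 4, before any re-treatment. The change should be made, but the trial's main criterion does not depend on it.

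**What to change.** Keep the offer and its trigger. In 6.5.3 and 6.6, state that a participant who takes the second treatment stays in follow-up and is neither withdrawn nor replaced for that reason. Add to section 7, before any results are seen:

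1. From the date of a second treatment, the tumour counts as not cleared by HIFU at later visits. For reduction of tumour mass, its last measurement before re-treatment is used.
2. Scarring, dyspigmentation and AE grade after month 3 are reported separately for HIFU-only and re-treated tumours (for an AE grade scored per participant, by whether the participant was re-treated). The last rating before re-treatment is shown for the re-treated.
3. The number, date and type of second treatments are reported by visit, with a sensitivity analysis that leaves re-treated tumours out.

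Check that the CRF records the date, tumour and type of each second treatment.

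The cost is a short paragraph, a sentence in 6.5.3 and 6.6, and at most a small CRF addition per tumour. There is no extra visit, the sample size does not change, and nobody loses treatment. Two drawbacks remain. Rule 1 may understate HIFU if a tumour would have kept shrinking; the sensitivity analysis shows how far the result depends on the rule but does not measure that understatement. Late HIFU scarring in a re-treated tumour cannot be separated from scarring caused by the second treatment.
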